- 311 addition of steroid to an anti-VEGF treatment regimen in eyes that have persistent DME despite

312	anti-VEGF treatment increases visual acuity and decreases DME in the short term, compared
313 314	with continued anti-VEGF treatment alone.
314 315	1.2 Study Objectives
315	1.2 Study Objectives To assess the short-term effects of combination steroid+anti-VEGF therapy on visual acuity and
317	retinal thickness on OCT in comparison with that of continued anti-VEGF therapy alone in eyes
318	with persistent central-involved DME and visual acuity impairment despite previous anti-VEGF
319	treatment.
320	
321	Furthermore, this phase II study is being conducted (1) to determine whether the conduct of a
322	phase III trial has merit based on functional and anatomic outcomes, (2) to estimate recruitment
323	potential of a phase III investigation, (3) to provide information needed to design a phase III trial,
324	and (4) to assess the safety of administering combination steroid+anti-VEGF therapy in eyes
325	with persistent DME. The study is not designed to definitively establish the efficacy of
326	corticosteroid+anti-VEGF therapy in the treatment of persistent central-involved DME.
327	
328	1.3 Study Design and Synopsis of Protocol
329	
330	A. Study Design
331	
332	• Randomized, controlled phase II multi-center clinical trial
333	
334	B. Major Eligibility Criteria
335	
336	• Age ≥ 18 years
337	• Type 1 or type 2 diabetes
338	• The study eye must meet the following criteria:
339	> Visual acuity letter score in study eye ≤ 78 and ≥ 24 (approximate Snellen
340	equivalent 20/32 to 20/320)
341	Ophthalmoscopic evidence of center-involved DME
342	OCT CSF thickness value (microns):
343	■ Zeiss Cirrus: ≥290 in women; ≥305 in men
344	■ Heidelberg Spectralis: ≥305 in women; ≥320 in men
345	At least three intravitreal anti-VEGF injections given within the prior 20 weeks
346	> No previous history of glaucoma or steroid intraocular pressure response in either
347	eye
348	
349	C. Run-In Phase
350	All potential study participants will be required to participate in a 12-week run-in phase. In order
351	to enter the run-in phase, all eligibility criteria must be assessed and met. During the run-in phase,
352	study eyes will receive 3 study ranibizumab 0.3mg injections approximately 4 weeks apart.
353	
354	At the end of the run-in phase (12-week visit), eyes with persistent DME despite prior intravitreal

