355	anti-VEGF therapy that still meet eligibility criteria (see section 4.2) will be randomized.
356	"Persistent DME" at end of the run-in phase is defined as meeting all of the following:

257	CEE this langes (mission) on OCT meeting with an one of the fallowing true conden
357	CSF thickness (microns) on OCT meeting either one of the following two gender
358	and OCT machine-specific criteria:
359	• Zeiss Cirrus: ≥ 290 in women; ≥ 305 in men
360	• Heidelberg Spectralis: \geq 305 in women; \geq 320 in men
361 362	Visual acuity letter score ≤ 78 and ≥ 24 (approximate Snellen equivalent 20/32 to 20/320)
363	 DME is the cause of OCT thickening and vision loss by the investigator's
363 364	
365	judgment
	D. Tucotmont Cuoung
366 367	D. Treatment Groups
	Eligible study eyes at the end of the run-in phase will be assigned randomly (1:1) to one of the
368	following groups:
369 370	• Crown A. Shorn Lintrovitroal ramihizurrah
	Group A: Sham + intravitreal ranibizumab
371 372	Group B: Intravitreal dexamethasone +intravitreal ranibizumab
373	Study participants may have one or two study eyes. Study participants with two study eyes will
374	be randomized to receive continued anti-VEGF therapy (ranibizumab) in one eye and
375	
376	dexamethasone +ranibizumab in the other eye.
377	For both treatment groups, the initial ranibizumab injections must be given on the day of
378	
	randomization. The sham or dexamethasone injection will be given within 0-8 days of the
379	ranibizumab injection. Study eyes will be evaluated for retreatment every 4 weeks based on OCT
380	and visual acuity. Further details on the treatment schedule and criteria for retreatment are
381 382	included in section 4.8.
383	E. Sample Size
384	A minimum of 150 study eyes (from approximately 125 participants assuming 20% have two
385	
385	study eyes)
387	F. Duration of Follow-up
388	 Definition of Fonov up 12-week run-in phase prior to randomization
389	
390	• Primary outcome at 24 weeks after randomization
390 391	G. Follow-up Schedule
392	 Follow-up visits occur every 4±1 weeks
392 393	• Tonow-up visits occur every 4±1 weeks
393 394	H. Main Efficacy Outcomes
395	II. Main Encacy Oucomes
396	At 24 weeks after randomization:
397	
398	Primary:
399	Mean change in visual acuity letter score, adjusted for visual acuity at time of
400	randomization
401	
402	Secondary:

403		• Percent of eyes with at least 10 and at least 15 letter gain (increase) or loss
404		(decrease) in E-ETDRS letter score visual acuity

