1211 1212 1213 1214 1215	The approach to sample size and statistical analyses are summarized below. A detailed statistical analysis plan will be written and finalized prior to the completion of the study. The analysis plan synopsis in this chapter contains the framework of the anticipated final analysis plan.
1213 1216 1217 1218 1219 1220 1221 1222	This phase II clinical trial is conducted to assess the short term effect of combination steroid + anti-VEGF therapy on visual acuity and OCT retinal thickness, in comparison with that of continued anti-VEGF therapy alone, in eyes with persistent central-involved DME and visual acuity impairment despite previous anti-VEGF treatment. The primary outcome of the study will be the mean change in visual acuity at the 24-week post-randomization visit, adjusted for the baseline (randomization) visual acuity.
1222	The treatment groups include the following:
1224	• Group A: Sham + intravitreal ranibizumab 0.3 mg
1225	• Group B: Intravitreal dexamethasone +intravitreal ranibizumab 0.3 mg
1226	
1227	7.1 Sample Size
1228	This phase II study will include 75 study eyes (from approximately 62 participants) in each
1229	treatment group.
1230	
1231	The primary analysis consists of a statistical estimation of the difference in mean change in visual
1232	acuity letter score at the 24-week post-randomization visit, adjusted for the baseline visual acuity
1233 1234	and correlation between eyes, between the sham + ranibizumab group and the combination of corticosteroid+ ranibizumab group.
1234	concosteroid+ ramoizumao group.
1235	7.2 Sample Size Assumptions and Precision Estimates
1230	To estimate the standard deviation (SD) of change in visual acuity from baseline (randomization)
1238	to the 24-week visit (primary outcome visit), data from the DRCR.net Protocol I were reviewed.
1239	Of eyes that completed the 1-year visit, 61 eyes were identified at the 32-week visit to have 1)
1240	OCT CSF≥250 µm, 2) VA between 20/320 to 20/32; and 3) received at least 3 ranibizumab
1241	injections from the 16-week visit to prior to the 32 week-visit. All these eyes had received at least
1242	3 ranibizumab injections prior to the 16-week visit and met the OCT and VA thresholds above,
1243	mimicking the minimum number of injections required for enrollment into the run-in phase of this
1244	protocol. The mean change in visual acuity letter score from the 32-week visit (to mimic

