1245	randomization visit of this protocol) to the 52-week visit (to mimic the 24-week visit of this
1246	protocol) for these 61 eyes, adjusted for baseline visual acuity, was +1.9 (95%CI: +0.1 to +3.7).
1247	The standard deviation for the mean change in visual acuity letter score adjusted for correlation
1248	with baseline visual acuity value was 6.9 letter score (95% CI: 5.9 to 8.4).
1249	
1250	The following table shows half-widths of 95%CI on the difference in mean visual acuity change

- between treatment groups for a range of SDs and sample sizes. For the sample size in each group
- 1252 of 70 (increased to 75 for approximately 5% lost to follow-up) that will be used, a two-sided 95%
- 1253 CI for the difference of the two means in visual acuity change from randomization to 24-week visit
- 1254 will extend 2.3 visual acuity letter score in either direction from the observed difference in means,
- assuming that the common standard deviation is a letter score of 7 (~the midpoint for the estimated
- 1256 standard deviation), not adjusting for correlation between eyes in participants with two study eyes.

- 1257 Similarly, half-width of the 95% CI using a standard deviation of 9 (~ the upper confidence limit
- 1258 for the estimated standard deviation) will be a letter score of 3.0. Adjustment in the primary
- 1259 analysis for between-eye correlation is expected to slightly reduce the expected width of the 1260 confidence interval over the tabled values.
- 1260
- Based on the above information, with an alpha of 0.05, if the true visual acuity mean difference is
- 1263 5 letters and the standard deviation is 9 then there is 90% power to detect a difference in visual
- acuity change between treatment groups.
- 1265

Standard Deviation	Sample Size Per Group				
	25	50	70	100	125
6	3.3	2.4	2.0	1.7	1.5
7	3.9	2.7	2.3	1.9	1.7
8	4.4	3.1	2.7	2.2	2.0
9	5.0	3.5	3.0	2.5	2.2
10	5.5	3.9	3.3	2.8	2.5
11	6.1	4.3	3.6	3.0	2.7

4.0

3.3

3.0

1266 Half-Width of a 95% Confidence Interval for the Difference in Mean visual acuity Change

1267

1268 **7.3 Efficacy Analysis Plan**

12

1269 7.3.1 Primary Outcome Analysis 1270 The primary analysis consists of the estimation of the difference in mean change between the

6.7

treatment groups in visual acuity letter score from randomization to the 24-week postrandomization visit, adjusted for randomization visual acuity and correlation between eyes of participants with two study eyes.

4.7

1274

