 - Report adjusted treatment group mean difference and 95% confidence interval from treatment group comparison within each subgroup. Only in the presence of a significant interaction term (*P*<0.05) the within-group *P*-value will be reported.
 - The effect of gender and race/ethnicity will be explored in the same way as the subgroup factors listed above. [not in text]
- iii. Secondary outcomes [Table 2]:
 - Binary outcomes: Perform binomial regression models with adjustment for same covariates in the primary analysis and use

generalized estimating equations to account for correlation between eyes of bilateral participants. All will be analyzed using imputed data (*%MIAnalyzeBinary* macro).

- When binomial regression model failed to converge, a hierarchy is used to remove the covariates: laterality → improvement in visual acuity during run-in phase → randomization visual acuity letter score.
 - This hierarchy was chosen based on judgment regarding theorized existence and strength of association with the outcome (least important → most important)
- Report the observed No. (%) by treatment group, adjusted difference in proportions, 95% confidence interval, and *P*value from treatment group comparisons
- AUC outcome: Mimic the linear mixed effect model in the primary analysis limiting the cohort to 24-week completers. No imputation will be performed.
 - Report mean ± SD and median [IQR] by treatment group, adjusted mean difference, 95% confidence interval, and *P*value from treatment group comparison.
- 5. Describe OCT Central Subfield Thickness at 24 weeks by treatment group
 - a. Report descriptive statistics using observed data in *visitEyesRand* dataset [Table 2]
 - i. Central subfield thickness at 24 weeks
 - Mean \pm SD
 - Median [IQR]
 - No. (%) of eyes below gender and OCT machine-specific values
 - Defined as <290 in women and <305 in men in Zeiss Cirrus; <305 in women and <320 in men in Heidelberg Spectralis
 - No imputation will be performed for this outcome. The analysis will include observed data only.
 - ii. Mean truncated change at 24 weeks from randomization
 - Mean \pm SD
 - Median [IQR]
 - No. (%) of eyes ≥ 1 logOCT step improvement, ≥ 2 logOCT steps improvement, ≥ 1 logOCT step worsening, ≥ 2 logOCT steps worsening
 - Footnote No. of missing values and No. of values truncated at 3 standard deviation from the mean (if any)¹

- iii. Area under the curve (AUC) between randomization and 24 weeks using truncated data [Figure 3]

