- Report the observed No. (%) by treatment group, adjusted difference in proportions, 95% confidence interval, and *P*value from treatment group comparisons
- AUC outcome: Mimic the linear mixed effect model in the primary analysis limiting the cohort to 24-week completers. No imputation will be performed.
 - Report mean ± SD and median [IQR] by treatment group, adjusted mean difference, 95% confidence interval, and *P*-value from treatment group comparison.
- 6. Summarize safety events occurred at any time during randomization phase
 - a. Ocular adverse events [eTable 5]
 - i. Tabulate No. (%) of eyes experienced at least one event by treatment group using *eyesRand* dataset
 - At least one ocular adverse events in the study eye
 - Increased intraocular pressure (IOP) events (a composite outcome, defined as any of the below). Each component will also be reported separately.
 - IOP increased \geq 10 mmHg from randomization at any visit
 - \circ IOP \geq 30 mmHg at any visit
 - Received ocular anti-hypertensives
 - Endophthalmitis
 - Inflammation
 - Any retinal detachment (a composite outcome, defined as any of the below). Each component will also be reported separately.
 - Traction retinal detachment
 - Rhegmatogenous retinal detachment
 - Unspecified retinal detachment
 - Retinal tears

- Retinal hemorrhage
- Vitreous hemorrhage
- Cataract extractions
- Glaucoma surgery
- Received post-injection treatment to lower IOP
- Migration of dexamethasone implant to the anterior chamber and subsequent corneal complications (combination group only)
 - Note: There is no specific MedDRA term for this type of adverse event. Instead, perform a manual check by searching for keywords "migration" and "anterior chamber" in the description field on the AE form, limiting to records in randomized eyes at post randomization.
- ii. Compare the frequency between treatment groups using Fisher's exact test and report *P*-value.
- iii. Footnote No. of patients experienced multiple types of ocular adverse events as listed above (if any)
- b. Systemic adverse events
 - i. All systemic adverse events will be reported by treatment group: combination group (unilateral participants), ranibizumab group (unilateral participants), and bilateral participants.
 - ii. Reduce *eyesRand* dataset to patient-level as a temporary dataset *ptRand*
 - iii. Tabulate No. (%) of participants experienced at least one event [eTable 6]
 - At least one systemic adverse event

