 - At least one serious systemic adverse event
 - At least one hospitalization
 - Death
 - APTC cardiovascular/cerebrovascular event (a composite outcome)
 - Non-fatal myocardial infarction
 - Non-fatal stroke
 - Death of vascular or unknown cause
 - iv. Compare frequency among unilateral participants between treatment groups using Fisher's exact test and report *P* value. [eTable 6]
 - v. Tabulate No. (%) of participants had at least one adverse event in each MedDRA system organ class [eTable 7]

References

 Tukey JW. The Future of Data Analysis. Ann. Math. Statist. 1962; 33(1):1-67. https://projecteuclid.org/euclid.aoms/1177704711#ui-tabs-1. Accessed 21 September 2017. 2. Schafer J. Multiple Imputation: A Primer. *Statistical Methods in Medical Research*. 1999(8):3-15.

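### Safety events are compared by Fisher P-value beside counts and percentages, with no planned risk difference or confidence interval

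*SAP*

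**What the plan says.** Protocol 1.2 lists as its fourth purpose "to assess the safety of administering combination steroid+anti-VEGF therapy in eyes" with persistent DME. Protocol 7.5 says only that events will be tabulated and compared, and defers the analytic approach to the detailed SAP.

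SAP item 6 supplies that approach:

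- **Ocular events (6.a, eTable 5).** Number and percentage of eyes with each event by group, then "Compare the frequency between treatment groups using Fisher's exact test and report" the P-value.
- **Systemic events (6.b, eTable 6).** Number and percentage of participants in three groups (unilateral combination, unilateral ranibizumab, bilateral), then "Compare frequency among unilateral participants between treatment groups using Fisher's exact test and report" the P-value.

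Neither step asks for a risk difference, a ratio or an interval. For binary efficacy outcomes (items 4.b.iii and 5.b.iii) the same SAP asks for the observed counts, an adjusted "difference in proportions, 95% confidence interval, and" a P-value, with generalized estimating equations for bilateral participants.

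**The concern.** Protocol 7.1 and 7.3.1 describe the primary analysis as estimation, and 7.2 works out precision for visual acuity. No power or precision is stated for any safety event, and safety is also where the planned comparison is a test alone. A P-value above 0.05 in a small trial does not show how large an excess of harm the data leave open. That upper limit is what someone weighing a longer phase III trial would want to know. The point is separate from the pairing of eyes: it applies equally to the systemic comparison, which is restricted to unilateral participants and so has independent groups.

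**Working it through.** **Group sizes.** The synopsis gives "A minimum of 150 study eyes (from approximately 125 participants assuming 20% have two" study eyes; Protocol 7.1 gives 75 eyes per group.

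- Bilateral participants: 125 × 0.20 = 25. Unilateral: 125 × 0.80 = 100.
- Eyes: 100 + 2 × 25 = 150, or 75 per group.
- Unilateral participants per group at 1:1: 100 / 2 = 50.

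The 62 participants per group in Protocol 7.1 is 125 halved. Bilateral participants contribute one eye to each group, so this does not change the 50.

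**The plan's own figure first.** Protocol 7.2 states 90% power for a 5-letter difference, SD 9, alpha 0.05, with 70 evaluable eyes per group.

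- Standard error: 9 × √(2/70) = 1.521. Ratio: 5 / 1.521 = 3.287.
- Power: Φ(3.287 − 1.960) = Φ(1.327) = 0.908 (noncentral t: 0.904).
- Half-width at SD 9: 1.960 × 1.521 = 2.98, against the stated 3.0.

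The efficacy figures reproduce and are not in dispute. There is no safety figure to reproduce.

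**Fisher power.** This is the sum, over all pairs of event counts with two-sided Fisher P<0.05, of the product of the two binomial probabilities. Eyes are treated as independent, as Fisher's test does. Rates are assumptions unless a source is given.

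| Per group | Ranibizumab v combination | Power |
|---|---|---|
| 50 participants | 10% v 20% | 19.5% |
| 50 participants | 5% v 15% | 24% |
| 50 participants | 5.2% v 10.4% | 7% |
| 50 participants | 5.2% v 15.6% | 26% |
| 75 eyes | 10% v 20% | 32% |
| 75 eyes | 5% v 15% | 44% |
| 75 eyes | 2% v 12.6% | 63% |
| 75 eyes | 10% v 25.5% | 64% |
| 75 eyes | 5% v 25.5% | 94% |

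The 5.2% is the sham-group Antiplatelet Trialists' Collaboration rate in the pooled trials of Protocol 6.5.1.1, doubled and tripled for illustration; using it as this trial's 24-week control rate is an assumption. The 12.6% (pressure rise of at least 10 mmHg after a first implant) and 25.5% (pressure-lowering medication started within 180 days) come from the vein-occlusion data in Protocol 6.5.1.2.

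With no control events, at least 6 combination events are needed for P<0.05: 12% of 50 or 8% of 75.

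**What an interval would add.** Newcombe's 95% interval for d = p₁ − p₀ uses each group's Wilson limits (l, u): lower d − √[(p₁−l₁)² + (u₀−p₀)²], upper d + √[(u₁−p₁)² + (p₀−l₀)²].

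For 3 v 3 of 50, p = 0.06 with Wilson limits 0.0206 and 0.1622. The upper limit is √(0.1022² + 0.0394²) = 0.109, and the interval is symmetric.

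| Combination v ranibizumab (hypothetical counts) | Fisher P | Difference, points (95% CI) |
|---|---|---|
| 3 v 3 of 50 | 1.0 | 0 (−10.9 to 10.9) |
| 0 v 0 of 50 | 1.0 | 0 (−7.1 to 7.1) |
| 8 v 3 of 50 | 0.20 | 10.0 (−2.8 to 23.1) |
| 5 v 0 of 50 | 0.056 | 10.0 (0.9 to 21.4) |
| 9 v 2 of 75 eyes, pairing ignored | 0.056 | 9.3 (0.7 to 18.8) |

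The first two rows carry the point: P=1.0 looks reassuring while the data exclude little.

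**The case against.** **The tables are not P-values alone.** A reader might infer that they are. In fact counts and percentages by group stand in the same eTables, so a crude difference can be obtained by subtraction. For unilateral participants the interval can be worked out too. This objection stands for the systemic table, where the gap is a missing planned summary and not lost information. It does not hold for eyes: about 25 participants give one eye to each group, so a valid interval cannot be recovered from the marginal counts.

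**The test is not blind to every harm.** It is tempting to say that most safety P-values will exceed 0.05 whatever the truth. The protocol's own implant figures contradict that for pressure. Besides 94% power for 5% v 25.5%, the 32.8% of eyes with two implants that had a rise of at least 10 mmHg over 12 months gives 99.5% power against an assumed 5% and 91% against 10%. The limitation concerns systemic, rare and moderately frequent events.

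**The near-0.05 examples mix methods.** Fisher's test is conservative, and the exact conditional odds-ratio interval that matches it includes 1 in both: 0.95 to infinity for 5 v 0 of 50, and 0.97 to 48.5 for 9 v 2 of 75. Those two rows therefore do not show harm that the test wrongly missed. This stands, and the argument does not rest on them.

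**Misreading is conjecture.** Nothing in the documents says that P>0.05 will be reported as no added risk. Protocol 7.6 does not list safety P-values among the phase III inputs, and the monitoring committee reviews adverse events about every six months. This limits the severity, but safety remains a stated purpose.

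**Another SAP exists.** The SAP overview cites a separate protocol SAP that was not supplied, and it may ask for intervals. A reader should not infer that no interval was ever planned for this trial.

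**Conclusion.** The point holds for the supplied plan. The between-group safety comparison is a Fisher P-value beside counts and percentages, with no planned effect estimate or interval, while binary efficacy outcomes have both. At the planned sizes the P-value is weakly informative for moderate excesses (about 20% power for 10% v 20% with 50 participants per group, 44% for 5% v 15% with 75 eyes), and P=1.0 can coexist with an excess of about 11 points. Large pressure excesses would probably be found.

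These figures assume the planned 125 participants with 20% bilateral, the event rates shown, and independent eyes. Protocol 7.2 expects adjustment for between-eye correlation to narrow the visual acuity interval slightly; the ocular intervals here make no such adjustment.

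No test is invalid and no stated number is wrong. This is a worthwhile, inexpensive reporting improvement that serves a stated purpose of the trial.

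**What to change.** In SAP 6.a.ii and 6.b.iv, report the risk difference (combination minus ranibizumab) with a 95% confidence interval beside the counts, percentages and P-value.

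- **Unilateral participants (6.b.iv):** a Newcombe or score interval.
- **Eyes (6.a.ii):** an interval that accounts for the correlation between the two eyes of bilateral participants, such as the binomial model with generalized estimating equations already planned for binary efficacy outcomes. Name an exact or score fallback in advance for sparse events.
- **Interpretation:** state that the interval is the main summary, that it may disagree with the conservative Fisher P near 0.05, and that P>0.05 will not be described as absence of a difference.

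If the separate protocol SAP already asks for intervals, reconcile the two documents.

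The cost is SAP wording and one extra column in eTables 5 and 6, with no new data. The downside is wide intervals for rare events, which show how little the trial can exclude.
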